Radiation risk: CT scans, x-rays (after flexible bronchoscopy), gastric emptying study, cardiac catheterization, invasive cardiopulmonary exercise testing and (potentially) lumbar puncture involve radiation. We estimate the additional amount of radiation that a patient will receive as a result of participating in this study will likely be a maximum of approximately 39 mSv over four years (if the participant undergoes all tests involving radiation), which is comparable to 13 times the yearly dose from natural environmental radiation in the US (3.1 mSv). This is well within the annual limits of 50 mSV set by the FDA for individuals participating in basic research studies. Radiation has been shown to cause cancer from exposures that are higher than the additional annual radiation dose received by participating in this study. According to the International Commission on Radiological Protection (ICRP), the increased risk of health effects, such as cancer, from radiation doses of this amount is either too small to be observed or nonexistent.

CT Scans: Some CT scans use iodinated contrast dye. Risks of contrast dye include allergic reaction and kidney damage. Kidney damage is usually mild and temporary.

MRI/MRV/MRA: MRI does not involve high-energy radiation but poses risk for people with metal implants, which may cause burns if the patient is not properly excluded from having the study. Patients may experience claustrophobia, difficulty breathing, hear loud noises, feel warm or hot, or experience tingling during the MRI. Very rarely, patients may experience burns even without metal in the body. Some subjects may experience nausea, dizziness, or have allergies to the gadolinium dye used to generate MRI contrast images. In rare situations, MRI dye can cause nephrogenic systemic fibrosis. Sites will follow the most current version of the American College of Radiology Manual on Contrast Media or local policies, whichever are more restrictive, to determine what (if any) pre-test testing is required, and if contrast can be safely administered, prior to completion of any test with gadolinium. There may also be risks associated with the use of electrocardiogram (see above).

Nerve conduction study (NCS) and electromyography (EMG): Either of these tests may cause mild patient discomfort, including tender muscles, because of the electrical signals (NCS) and tiny needles

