Site staff are ultimately responsible for ensuring participants do not meet safety exclusion criteria after they have been selected for a test, as not all exclusion criteria are available in REDCap. Pre-test assessments that are conducted once participant is assigned to a test to determine safety exclusion criteria must then be documented in REDCap. SOPs for these tests make clear that ineligible participants might be assigned tests because not all exclusion information is known to REDCap. These safety exclusion criteria are also

available as checklists for site staff in the respective SOP. For all Tier 3 tests that are more than minimal risk, a licensed physician will review the exclusion criteria for that test and confirm that the subject does not meet any of the specified safety exclusion criteria.

Procedures in Tier 3 will only be performed concurrently when clinically appropriate. Complete information regarding how tests will be assigned will be in each assessment's SOP. Tier 2 and 3 procedure eligibility, exclusion criteria, and clinical variance affecting the risk/benefit assessment are found in **Appendix 5**: Tier 2 and 3 eligibility, exclusion criteria.

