Symptoms	Color changes in your skin, such as red, white or purple and details	At enrollment and every 3 months thereafter

Category	Element	Interval
Symptoms	Skin rash	At enrollment and every 3 months thereafter
Symptoms	Changes in sweating	At enrollment and every 3 months thereafter
Symptoms	Excessively dry eyes	At enrollment and every 3 months thereafter
Symptoms	Excessively dry mouth	At enrollment and every 3 months thereafter
Symptoms	Excessive thirst	At enrollment and every 3 months thereafter
Symptoms	Vision problems (blurry, light sensitivity, difficulty reading or focusing, floaters, flashing lights, "snow") and details	At enrollment and every 3 months thereafter
Symptoms	Problems with hearing (hearing loss, ringing in ears) and details	At enrollment and every 3 months thereafter
Symptoms	Hair loss	At enrollment and every 3 months thereafter
Symptoms	Problems with teeth or gums	At enrollment and every 3 months thereafter
Symptoms	Change in menstruation or menopause and details	At enrollment and every 3 months thereafter
Symptoms	Changes in desire for, comfort with or capacity for sex	At enrollment and every 3 months thereafter
Change in symptoms since infection	Changes in symptoms reported before and after index date	Once, at second visit or most recent visit if implemented after
Post-COVID utilization	Hospitalization since COVID or last assessment	At enrollment and every 3 months thereafter
Post-COVID utilization	Emergency department visit since COVID or last assessment	At enrollment and every 3 months thereafter
Clinical assessment	Height, weight, BMI	0, 6 months after infection then yearly
Clinical assessment	Waist circumference (cm)	0, 6 months after infection then yearly
Clinical assessment	Seated vital signs (blood pressure, heart rate, respiratory rate, oxygen saturation)	0, 6 months after infection then yearly
Clinical assessment	30 second sit to stand	0, 6 months after infection then yearly
Clinical assessment	Active standing test	0, 6 months after infection then yearly
Clinical assessment	Capnography	0, 6 months after infection then yearly
Clinical assessment	Wearable with continuous remote monitoring for ECG, RR, SpO2, sleep fragmentation, actigraphy	Continuous

Category	Element	Interval
Laboratory study	Comprehensive metabolic panel with cystatin-C	0, 3, 6 months after infection then yearly if abnormal
Laboratory study	Complete blood count with differential	0, 3, 6 months after infection then yearly if abnormal

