Brain MRI or Brain MRI with gadolinium	3	All participants are eligible for this test through random assignment. Participants with relevant symptoms (as outlined in the applicable SOP) will be oversampled for assignment as follows: ANY of the following: Abnormal NIH Toolbox or other cognitive test scores Headaches Abnormal autonomic testing Newly diagnosed PTSD, psychosis, prolonged grief, depression, or anxiety Tinnitus Newly diagnosed stroke Reduced smell functioning Mechanical ventilation during acute COVID	 Known contraindication to MRI examination (i.e., severe claustrophobia, pacemaker, defibrillator, neuro-stimulator, ferro-magnetic or unknown aneurysm clip, 3T MR incompatible metal implant of any kind or potentially dangerous foreign metal objects in the body such as bullets, shrapnel, metal slivers, etc.) Severe kidney disease depending on type of gadolinium used, or allergy to gadolinium Pregnant or < 3 months postpartum 	Permissible clinical variation: Apart from the absolute exclusion for retained metal, MRI exclusions are primarily dependent on the guidelines/practices of the local imaging site. Prior to scheduling participant for procedure, sites should follow local policy regarding any required pre-test labs. Sites that do not have a local policy that outlines pre-test requirements should follow American College of Radiology guidance. Choice of gadolinium-based contrast agent is dependent on local site availability. The MRI contrast agent and dosing administration use for the study

Procedure name(s)	Tier	Eligibility	Exclusion criteria	Additional information about test procedures and permissible clinical variation
				should be followed per local site procedures/policies. If a site has multiple contrasts available, the site should contact the MRI reading center regarding contrast selection and should use one contrast agent for the course of the study.
				Permissible clinical variation:

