Cardiac MRI or Cardiac MRI with gadolinium	3	All participants are eligible for this test through random assignment. Participants with relevant symptoms (as outlined in the applicable SOP) will be oversampled for assignment as follows: ANY of the following: Elevated cardiac markers Reduced ejection fraction Pericardial effusion Abnormal global longitudinal strain	 Known contraindication to an MRI examination (i.e., severe claustrophobia, pacemaker, defibrillator, neuro-stimulator, ferro-magnetic or unknown aneurysm clip, 3T MR incompatible metal implant of any kind or potentially dangerous foreign metal objects in the body such as bullets, shrapnel, metal slivers, etc.) Severe kidney disease depending on type of gadolinium used, or allergy to gadolinium Pregnant or < 3 months postpartum 	 Apart from the absolute exclusion for retained metal, MRI exclusions are primarily dependent on the guidelines/practices of the local imaging site. Prior to scheduling participant for procedure, sites should follow local policy regarding any required pre-test labs. Sites that do not have a local policy that outlines pre-test requirements should follow American College of Radiology guidance.⁵⁴ Choice of gadolinium-based contrast agent is dependent on local site availability. The MRI contrast agent and dosing administration use for the study should be followed per local site procedures/policies. If a site has multiple contrasts available, the site should contact the MRI reading center regarding contrast selection and should use one contrast agent for the course of the study. Additional information about test procedures:

Procedure name(s)	Tier	Eligibility	Exclusion criteria	Additional information about test procedures and permissible clinical variation
				A recent hematocrit (either 30 days before or 15 days after) the test is required for best interpretation of results.

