Flexible bronchoscopy with bronchoalveolar lavage and brushings, with or without (IV) procedural sedation	3	All participants are eligible for this test through random assignment. Participants with the following characteristics (as outlined in the applicable SOP) will be oversampled for assignment as follows: ANY of the following: Moderate to severe shortness of breath with normal chest CT Moderate to severe shortness of breath with abnormal chest CT	 Lack of safe discharge plan (needs adult companion at time of release) or reliable post-procedure contact Age > 70 years Age 60-70 years with ASA > 2 Resting room air oxygen saturation < 90% or < 88% at high altitude Hypoxia requiring > 2L nasal cannula at rest Untreated obstructive sleep apnea Severe pulmonary hypertension (mPAP ≥ 35) Systolic blood pressure > 180 mmHg or MAP < 50 Known elevated intracranial pressure Intrinsic bleeding disorder (liver failure, uremia, other known bleeding disorder, history of excessive bleeding during procedures), including those with the following abnormalities within 30 days of procedure: PTT > 1.5 times upper limit of normal INR > 1.3 times upper limit of normal Platelets < 100,000/mL Any of the following abnormal results within 30 days of procedure: 	 Choice of transoral or transnasal approach is at local clinician discretion and should consider patient factors. Delivery of topical lidocaine (gargle, aerosol, spray or instillation) is at local clinician discretion and should consider patient factors. Use of procedural sedation is at local clinician discretion and should consider patient factors. Use of procedural sedation is selected, personnel administering sedation, choice of sedation agents, dosage limits and intervals, and credentialing must be managed according to local institutional policy, but may not exceed limits indicated in the SOP. The choice of left or right side for specimen collection is at clinician discretion and should be tailored to chest CT findings Monitoring during and post-procedure must be conducted in accordance with local institutional policy. Additional information about test procedures Participants must fast for 6 hours prior to procedure

Procedure name(s)	Tier	Eligibility	Exclusion criteria	Additional information about test procedures and permissible clinical variation

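### Appendix 5 makes local policy the first rule for laboratory tests before gadolinium MRI, and so drops the ACR floor that Section 4.1 sets

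*Protocol*

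**What the plan says.** Section 4.1 (Known Potential Risks, MRI paragraph) states: "Sites will follow the most current version of the American College of Radiology Manual on Contrast Media or local policies, whichever are more restrictive". The sentence goes on to give its scope: "to determine what (if any) pre-test testing is required, and if contrast can be safely administered, prior to completion of any test with gadolinium". The ACR manual is therefore a minimum that local policy may exceed but not undercut.

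Appendix 5 (Section 19.5) has one row for brain MRI and one for cardiac MRI, each covering scans with and without gadolinium. Under permissible clinical variation, both rows say: "Prior to scheduling participant for procedure, sites should follow local policy regarding any required pre-test labs". The ACR comes next, as a fallback: "Sites that do not have a local policy that outlines pre-test requirements should follow American College of Radiology guidance". Neither row repeats the stricter-of-two condition or refers back to Section 4.1.

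Both rows list as an exclusion: "Severe kidney disease depending on type of gadolinium used, or allergy to gadolinium". Section 6.1 adds a physician check: "For all Tier 3 tests that are more than minimal risk, a licensed physician will review the exclusion criteria for that test".

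**The concern.** The protocol holds two current rules for the same decision, and they rank the ACR manual differently. In Section 4.1 it binds every site. In Appendix 5 it binds only sites that have no policy of their own.

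The decision concerns safety. Section 4.1 names nephrogenic systemic fibrosis as a rare consequence of MRI dye. The kidney exclusion and the physician review stand under either rule, but neither will reveal impaired kidney function that is not already known and has not been tested for. The MRI rows give no creatinine or eGFR value and no window for a kidney test, so the pre-test rule largely decides whether kidney function is measured before contrast.

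**Working it through.** There is no figure in the plan to reproduce. The check sets the two rules side by side for every kind of site.

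| Site's local policy on pre-test labs | Section 4.1 gives | Appendix 5 MRI rows give | Agree? |
|---|---|---|---|
| None | ACR | ACR | Yes |
| As strict as the ACR, or stricter | Local policy | Local policy | Yes |
| Less strict than the ACR | ACR | Local policy | No |

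The conflict is confined to the third line. That is the only case in which taking the stricter of the two rules adds anything to following local policy where it exists.

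**Which text would a site use?** Section 6.1 names Appendix 5 as the place for Tier 2 and 3 eligibility, exclusions and clinical variance that bears on risk and benefit. Section 6.1.2 says the SOPs are written to contain all the clinical variation the protocol permits, and Section 6.1 says the site safety checklists are in the SOPs. The rule that puts local policy ahead of the ACR sits under permissible variation, so it can pass into those SOPs. Section 4.1 is a narrative risk section.

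**Do other rows fix a kidney test?** Yes. The bronchoscopy row excludes creatinine above 2 mg/dL under the line "Any of the following abnormal results within 30 days of procedure". The right heart catheterization row uses the same limit within 21 days. The cardiac MRI row does set a hematocrit window (30 days before to 15 days after), but for interpreting the scan.

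**Does the Tier 1 metabolic panel fill the gap?** Not reliably. Appendix 2 schedules it at "0, 3, 6 months after infection then yearly if abnormal". I read this as no required repeat when the result is normal. Appendix 1 allows Tier 3 tests at every visit to month 48. For a participant whose month 6 panel was normal, the time from the last required panel to a gadolinium scan is the scan month minus 6:

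- scan at month 12: 12 − 6 = 6 months
- scan at month 24: 24 − 6 = 18 months
- scan at month 36: 36 − 6 = 30 months
- scan at month 48: 48 − 6 = 42 months

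These are illustrations for one kind of participant. Appendix 1 also marks a laboratory form at months 12, 24, 36 and 48. That does not show the panel is repeated then: in Appendix 2, hemoglobin A1c is due yearly whatever the result, while the metabolic panel is yearly only if abnormal. A participant who enrols later has a more recent baseline panel, and the interval is shorter.

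**The case against.** The strongest reply is that a site can obey both texts. If local policy is looser than the ACR's, doing the ACR testing satisfies Section 4.1 and breaches nothing in Appendix 5, which does not forbid extra tests. Section 4.1 uses mandatory wording and covers every gadolinium test, while the appendix wording is advisory and must also serve scans without contrast. This is fair as far as it goes. But a site has to know of Section 4.1 to reconcile the two, and the rows that govern the procedure do not point there.

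Second, the content of the ACR minimum is not visible. Section 4.1 itself allows that no testing may be required, the kidney exclusion depends on the agent, and Table 1 in Section 3.3 describes the current macrocyclic formulation as very safe. Whether a looser policy would in fact drop a test cannot be settled from the protocol. This stands, and it limits the size of the point.

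Third, other safeguards exist. Kidney disease is asked about at enrollment and every 3 months (Appendix 2), and pre-test safety assessments must be documented in REDCap (Section 6.1). These find known disease; they do not find silent disease. A gadolinium MRI is also done only once, or twice for a participant who crosses from uninfected to infected, so the intervals above are not repeated exposures.

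Last, the bronchoscopy and catheterization limits belong to invasive procedures and do not prove that MRI needs a fixed limit. Agreed: they show only that the protocol writes a kidney check into a row when it wants one there.

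**Conclusion.** The inconsistency is real and should be corrected. It affects gadolinium brain and cardiac MRI at sites whose own policy on pre-test labs is less strict than the ACR manual; at all other sites the two rules coincide. The number of such sites and participants is not given and could be zero. No endpoint, sample size, power or analysis is touched.

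The conclusion rests on the wording of the two sections alone. The claim that kidney impairment could be missed rests on two further assumptions that the protocol cannot confirm: that the ACR manual asks for a kidney test in some participants, and that some local policy does not. The panel intervals of 6 to 42 months are supporting illustration, and the finding does not depend on them.

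**What to change.** In both MRI rows of Appendix 5, replace the two sentences that put local policy ahead of the ACR with the Section 4.1 rule for any scan with gadolinium: the stricter of the current ACR Manual on Contrast Media and local policy decides both what pre-test testing is required and whether contrast may be given. Check the matching SOPs and checklists, which are not shown here, and change them if they give local policy the same priority.

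While editing the cardiac MRI row, correct its citation as well. It attaches reference 54 to the ACR guidance, and that entry is a histopathology study of muscle and nerve.

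The cost is one replacement sentence in two table rows, any SOP updates, and some added pre-test labs at sites with looser policies. Section 4.1 already requires those labs.
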